2.1.2 Omnipod Horizon™ ACE Pump

The Pod component of the Omnipod Horizon™ System is similar to the Omnipod® DASH ACE Pump cleared under K191679. Compared to the DASH ACE Pump (K191679), the Horizon™ ACE Pump (Pod) has additional software to optimize communication to accept inputs from the iCGM (initially the Dexcom G6) and the Horizon™ Controller. The insulin delivery mechanism and the patient and fluid contacting components are identical to the DASH Pod.

The Pod is a lightweight, self-adhesive device that the user fills with U-100 rapid-acting insulin and wears directly on their body. The Pod delivers insulin into the user's body through a small flexible tube, called a cannula, based on the commands from the compatible controller. In the Omnipod Horizon™ System, the Pod will house the MPC algorithm and communicate directly with the iCGM and the Horizon App. The algorithm commands the Pod's insulin delivery in the form of micro-boluses based on predicted glucose values. As with the cleared Omnipod® DASH System, the Pod of the Omnipod Horizon™ System will come pre-packaged in a sterile container with a fill needle and a fill syringe. **Figure 2** below is a representation of the Pod.

[figure not shown]

Figure 2: The Pod of the Omnipod Horizon™ ACE pump

2.1.3 iCGM

The third component of the Omnipod Horizon™ System is the iCGM. The Omnipod Horizon™ System will be interoperable with a compatible iCGM, currently the Dexcom G6 Continuous Glucose Monitoring System (K191450). The Omnipod Horizon™ Pod will communicate with the Dexcom G6 via Bluetooth Low Energy (BLE). Glucose values from the Dexcom transmitter will be sent to the MPC algorithm residing on the Pod and used in insulin dosing adjustments. The glucose values from the Dexcom transmitter will be sent independently to the Dexcom App on the controller.

2.1.4 CGM-informed Bolus Calculator

Omnipod Horizon™ will allow for ease of population of CGM values within the bolus calculator, to allow for safe and improved usability for the calculation of meal and correction boluses.

The system uses estimated glucose values from Dexcom's G6 iCGM to guide both the automatic insulin delivery algorithm in Automated Mode and in calculating correction boluses when initiated by the user in both Manual and Automated Mode.

3 HORIZON™ DATA PORTAL

Data are securely uploaded from the PDM to Insulet Cloud by cellular connection. Data are then transferred from Insulet Cloud to the Horizon Data Portal (HDP), which is a platform for data review and management. The HDP runs on an Amazon-based web server. The HDP will provide insights including but not limited to: time in range (with connected CGM), time at each target BG, automated/manual mode comparisons, and time spent in each mode.

Investigators will have access to all uploaded data and be able to view historical trends. The HDP will function as the data management review platform for this study.

4 RESULTS FROM FEASIBILITY STUDIES

The Omnipod Horizon™ System has been tested in 194 subjects across IDE G160169, G170012, G170143 yielding approximately 13,000 subject hours of hybrid closed-loop control. The study results were presented in part at ATTD 2017, 2018, ADA 2017, 2018, and 2019, and have also been published in Diabetes Technology and Therapeutics.^{13, 14, 15, 16, 17, 18, 19, 20, 21, 22, 23, 29}.

5 STUDY SUMMARY

5.1 Study Purpose

The purpose of this study is to assess the safety and effectiveness of the Omnipod Horizon™ System's CGM-informed bolus calculator in patients with type 1 diabetes during Manual Mode operation.

5.2 Study Design

This is a single-arm, multi-center, prospective clinical study. A total of up to 42 subjects aged 2-70 years with type 1 diabetes will be enrolled in the study in order to obtain a minimum of 30 evaluable. Subjects aged 6-70 may be recruited from the Omnipod Horizon™ Pivotal Study (G190270) prior to their recommencement of the pivotal study after study pause. Subjects aged 2-5.9 may be recruited from

the pivotal study but must complete, or withdraw from this study before commencement of the Standard Therapy phase of the preschool pivotal study.

The study schedule consists of two outpatient phases:

- 1) 7 days of Omnipod Horizon™ use in Manual Mode without a connected CGM using manual entry of BG values to deliver boluses (Phase 1) followed by;
- 2) 7 days of Omnipod Horizon™ use in Manual Mode with a connected CGM using the CGM-informed bolus calculator to deliver boluses (Phase 2)

Subjects will be enrolled across 4-7 clinical study sites. The 30 evaluable subjects will be comprised of three age cohorts as follows:

- 15 subjects aged 18-70 years
- 10 subjects aged 6-17.9 years
- 5 subjects aged 2-5.9 years

Following subject screening, and enrollment, subjects will commence the first 7-day Manual Mode phase of the study.

Subjects not currently enrolled in the Omnipod Horizon™ Pivotal Study (G190270) will train to use the Manual Mode feature of the system including how to use the bolus calculator using manual entry of BG values or by using the CGM-informed bolus calculator.

After completion of the first 7 days of the Manual Mode phase using the Omnipod Horizon™ without a connected CGM, subjects will transition to the next 7 days of the Manual Mode phase using the system with a connected CGM using the CGM-informed bolus calculator to deliver boluses.

Table 1 outlines the schedule of assessments for each phase of the study.

Table 1: Schedule of Assessments

Assessment Schedule	Screening	Horizon™ Manual Mode (MM)						EW ^a
		PHASE 1 7-days of MM (without CGM connected)		PHASE 2 7-days of MM (with CGM connected)				
Visit Number	1 ^e	2 ^e	3	4	5	6	UV ^b	
Study Day/Visit Window	Within 30 days prior to or same day as Phase 1 start ^g	1d	3d ±1d	8d ±1d	10 ±1d	14 ±1d	N/A	
Telephone (T) or Office (O) Visit	T/O ^h	T/O ^h	T/O ^d	T/O ^d	T/O ^d	T/O ^d	T/O ^d	T/O
Laboratory Assessments								
A1C (POC) ^g	X							
Pregnancy Test ⁱ	X							
Clinical Assessments								
Informed Consent	X							
Medical History (including demographics) ^g	X							
Confirm Eligibility	X							
Concomitant medications	X	X ^c	X ^c	X ^c	X ^c	X ^c	X ^c	X ^c
Height ^g	X							
Weight ^g	X							
Vital signs ^g	X					X		X
Adverse events		X	X ^c	X ^c	X ^c	X ^c	X ^c	X ^c

Assessment Schedule	Screening	Horizon™ Manual Mode (MM)						EW ^a
		PHASE 1 7-days of MM (without connected CGM)		PHASE 2 7-days of MM (with connected CGM)				
Visit Number	1 ^e	2	3	4	5	6	UV ^b	
Study Day/Visit Window	Within 30 days prior to or same day as Phase 1 start ^g	1d	3d ±1d	8d ±1d	10 ±1d	14 ±1d	N/A	
Telephone (T) or Office (O) Visit	T/O ^h	T/O ^h	T/O ^d	T/O ^d	T/O ^d	T/O ^d	T/O ^d	T/O ^d
Study Devices								
Training on Glucagon administration and information on treatment of hypo/hyperglycemia ^f		X						
Study device training Omnipod Horizon™ (including CGM), BG/Ketone meter ^f		X						
Dispense/Return Omnipod Horizon™ (including CGM), QC tested BG/Ketone meter ^f		X					X	X
Removal of subject's personal insulin pump ^f		X						
Placement of the Omnipod Horizon™ on body ^f		X						
Enrollment		X						
Pairing the CGM transmitter to the Dexcom App on the PDM				X				

Assessment Schedule	Screening	Horizon™ Manual Mode (MM)							EW ^a
		PHASE 1 7-days of MM (without connected CGM)			PHASE 2 7-days of MM (with connected CGM)				
Visit Number	1 ^e	2	3	4	5	6	UV ^b		
Study Day/Visit Window	Within 30 days prior to or same day as Phase 1 start ^g	1d	3d ±1d	8d ±1d	10 ±1d	14 ±1d	N/A		
Telephone (T) or Office (O) Visit	T/O ^h	T/O ^h	T/O ^d	T/O ^d	T/O ^d	T/O ^d	T/O ^d	T/O ^d	
Complaints/device deficiencies		X	X ^c	X ^c	X ^c	X ^c	X ^c	X ^c	
Data review			X	X	X	X	X	X	
BG/Ketone Device uploads				X ^d		X ^d	X ^d	X ^d	

Abbreviations: S=Screening; MM=Manual Mode; EW=Early Withdrawal; QC=Quality Control; UV=Unscheduled Visit

^aEarly withdrawal visit will be conducted for enrolled subjects that did not complete both Manual Mode phases.

^bUnscheduled visits will serve as extra study visits, if needed. All unscheduled visits must obtain the defined schedule of assessments. These visits should not be documented for appointment confirmation, device shipments, general inquiries, or for activities covered by other assessments.

^cDocumentation only applicable if there are changes from previous assessment.

^dVisits identified as "T/O" can either be conducted in person at the clinical site or over the telephone. If conducted over the telephone, vital signs and device uploads are not required. Visits identified as "O" can only be conducted in person at the clinical site.

^eVisit 1 and Visit 2 may occur on the same day - Any assessment required by both visits will only need to be completed once. All Visit 1 assessments do not need to occur on the same day as long as the assessments occur within 30 days prior to Visit 2, or for subjects currently enrolled in Omnipod Horizon™ Pivotal Study (G190270).

^fOnly applicable if subject is not currently enrolled in the Omnipod Horizon™ Pivotal Study (G190270).

^gFor subjects aged 6-70 currently enrolled in the Omnipod Horizon™ Pivotal Study (G190270), specified screening assessments are not required if they were done for the Pivotal study, and there are no significant changes from the Pivotal study screening assessments. For subjects aged 2-5.9 that plan to

participate in the Pivotal study, the specified screening assessments only need to be collected once as long as they are completed within the timeframe required by both studies.

^hFor subjects not currently enrolled in the Omnipod Horizon™ Pivotal Study (G190270) this visit must be conducted in person at the clinical study site.

ⁱIf subject is currently enrolled in the Omnipod Horizon™ Pivotal Study (G190270) and not able to attend in person, they may conduct the pregnancy test at home and report result to the site.

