--	--

	
16. Unable to follow clinical protocol for the duration of the study or is otherwise deemed unacceptable to participate in the study per the investigator's clinical judgment

Study schedule overview	
The study schedule consists of the following two outpatient phases:
 
 1) 7 days of Omnipod Horizon™ use in Manual Mode without a connected CGM using manual entry of BG values to deliver boluses (Phase 1) followed by; 2) 7 days of Omnipod Horizon™ use in Manual Mode with a connected CGM using the CGM-informed bolus calculator to deliver boluses (Phase 2) 
Following subject screening, system training and enrollment, subjects will commence Phase 1 of the study.
 
Subjects will be trained to use the Manual Mode feature of the system including how to use the bolus calculator using manual entry of BG values and by using the CGM-informed bolus calculator.
 
After completion of the first 7 days of the Manual Mode phase using the Omnipod Horizon™ without a connected CGM (Phase 1), subjects will transition to the next 7 days of the Manual Mode phase using the system with a connected CGM using the CGM-informed bolus calculator to deliver boluses (Phase 2). Upon completion of this study, subjects aged 6-70 previously enrolled in the Omnipod Horizon™ Pivotal Study (G190270) will recomment the pivotal study. Upon completion, or withdraw from this study, subjects aged 2-5.9 may commence the Standard Therapy phase of the preschool pivotal study.

GLOSSARY OF ACRONYMS

ACE	Alternate Controller Enabled
ADE	Adverse Device Effect
AE	Adverse Event
AGC	Automated Glucose Control
BG	Blood Glucose
BLE	Bluetooth Low Energy
CFR	Code of Federal Regulations
CGM	Continuous Glucose Monitoring
CRA	Clinical Research Associate
CRO	Contract Research Organization
CV	Curricula Vitae
DD	Device Deficiency
DKA	Diabetic Ketoacidosis
dL	Deciliter
eCRF	Electronic Case Report Form
EDC	Electronic Data Capture
FDA	Food and Drug Administration
GCP	Good Clinical Practice
HIPAA	Health Insurance Portability and Accountability Act
ICF	Informed Consent Form
IDE	Investigational Device Exemption
IRB	Institutional Review Board
ITT	Intention to Treat
MD	Doctor of Medicine
mg	Milligram
miITT	Modified Intention to Treat
mmol	Millimole
MM	Medical Monitor
MPC	Model Predictive Control
PDM	Personal Diabetes Manager
POC	Point of Care
PI	Principal Investigator
pMPC	Personalized Model Predictive Control
PP	Per Protocol

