7 SUBJECT SELECTION AND ELIGIBILITY

Potential subjects for this study will include individuals who have been diagnosed with type 1 diabetes for at least 6 months and are current or prior Omnipod users. Subjects aged 6-70 from the Omnipod Horizon™ Pivotal Study (G190270) may participate in this study during the study pause and must complete this study prior to their recommencement of the pivotal study. Subjects aged 2-5.9 may be recruited from the pivotal study but must complete or withdraw from this study before commencement of the Standard Therapy phase of the preschool pivotal study. Potential subjects will be selected at each clinical study site and screened accordingly. Every effort will be made to establish eligibility of the patient prior to enrollment. Only patients who appear to meet all eligibility criteria will be enrolled in the study. Subject eligibility will be confirmed by study staff during a screening visit. A point of care (POC) A1C will be used at screening to determine eligibility.

7.1 Visit 1

Visit 1 will be conducted either over the telephone or in person at the clinical study site. This visit will assess subject's eligibility and will include:

- Signing of informed consent/assent
- Review of inclusion/exclusion criteria
- Screening assessments performed following Table 1: Schedule of Assessments

Informed Consent

Subjects who appear to meet the eligibility criteria will be asked to sign an Informed Consent Form (ICF) approved by each respective Institutional Review Board (IRB) for participation in the study prior to completing any screening assessments. A parent/guardian must sign the ICF for subjects <18 years of age. Assent will be obtained from subjects aged <18 years per State requirements. Failure to provide informed consent/assent will render the subject ineligible for the study. Due to utilizing screening assessments for subjects aged 6-70 years that are participating in the Omnipod Horizon™ Pivotal Study, the date of consent for this study will occur much later than the date of the screening assessments.

Due to restrictions in place for the COVID-19 pandemic, sites may perform the informed consent process over the telephone per their site's procedures.

Subjects must also have a signed HIPAA (Health Insurance Portability and Accountability Act) release of protected health information (PHI). The release may be a stand-alone document or part of the informed consent.

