8 OMNIPOD HORIZON™ MANUAL MODE

The Omnipod Horizon™ Manual Mode will consist of two outpatient phases:

1. 7 days of Omnipod Horizon™ use in Manual Mode without a connected CGM using manual entry of BG values to deliver boluses (Phase 1) followed by;
2. 7 days of Omnipod Horizon™ use in Manual Mode with a connected CGM using the CGM-informed bolus calculator to deliver boluses (Phase 2)

Enrollment

Subjects who meet all eligibility criteria and have completed all screening assessments will continue to enrollment. A subject is enrolled in the study at the commencement of Visit 2. Subjects that do not meet the eligibility criteria will not continue in the study and will be considered screen failures.

If for any reason a subject is no longer eligible for the study before enrollment, the subject will not continue in the study. No additional study assessments will be required. The reason for study exit will be clearly documented.

8.1 Phase 1

8.1.1 Visit 2

Visit 2 represents the commencement of the first 7 days of Manual Mode (Phase 1) and will be conducted either over the telephone or in person at the clinical study site on Day 1. This visit will include:

- Review of concomitant medications
- Assessment of adverse events
- Training on Glucagon administration and information on treatment of hypo/hyperglycemia (if training was not previously performed while participating in the Omnipod Horizon™ Pivotal Study (G190270)
- Study device training per manufacturer's instructions (BG and ketone meters), (if training was not previously performed while participating in the Omnipod Horizon™ Pivotal Study (G190270)
- Omnipod Horizon™ System device training conducted by trained clinical site staff (if training was not previously performed while participating in the Omnipod Horizon™ Pivotal Study (G190270)
 - Subjects will be trained on operating Omnipod Horizon™ in Manual Mode.
 - This will include first time device set-up with entry of basal profile, bolus calculator settings with insulin:carbohydrate ratio, target

glucose and correction factor. Subjects should enter settings similar to their usual settings as appropriate.

- The Pod will be filled with the subject's own U-100 rapid-acting insulin and placed on body.

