- Subjects will also be trained on use of Dexcom G6 CGM, setting up low (recommended to be 70 mg/dL or higher) and high glucose alerts (recommended to be 300 mg/dL or lower), setting up Dexcom Follow as desired, and calibrating their CGM as required, per the manufacturer's instructions
- Subjects will be trained to use the Bolus Calculator, entering in estimated carbs for meals and manually entering a BG value
- Subjects may choose their desired target BG ranging between 110-150 mg/dL in increments of 10 mg/dL for the bolus calculator

- Dispense Omnipod Horizon™ System, including CGM (if System was not previously dispensed while participating in the Omnipod Horizon™ Pivotal Study (G190270))
- QC testing of BG and ketone meter (if devices were not previously dispensed while participating in the Omnipod Horizon™ Pivotal Study (G190270))
 - Must pass as least one level of quality control testing prior to dispensing. QC testing may occur at any time prior to dispensing to subject.
- Removal of the subject's personal insulin pump (if not currently using the Omnipod Horizon™ System in Manual Mode)
 - Investigators should use the Insulet-provided Patient Therapy Order Form (PTOF) to document pump settings (Appendix A)
- Placement of the Omnipod Horizon™ on body (if not currently using the Omnipod Horizon™ System in Manual Mode)
- CGM sensor placement (if not currently wearing Omnipod Horizon™ study CGM)
 - Approved anatomical locations for CGM sensor placement will be reinforced as well as the importance of using approved locations
- Assessment of complaints and/or device deficiencies
- Each subject will initiate their treatment marking their commencement of the first 7 days of Manual Mode (Enrollment and Phase 1).

Subjects will be dispensed the following devices and supplies (if not currently enrolled in the Omnipod Horizon™ Pivotal Study (G190270)):

- Omnipod Horizon™ PDM and Pods
- Dexcom transmitter
- Dexcom sensors
- Contour® Next One blood glucose meter
- Contour® Next One blood glucose meter test strips
- Lancets
- Precision Xtra blood ketone meter
- Precision Xtra blood ketone meter test strips

During the first 7 days of Manual Mode, subjects will be instructed to:

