- Use the bolus calculator to administer meal boluses for all meals when carbohydrates are consumed as well as to administer correction boluses, when desired. For meal boluses, subjects will estimate the grams of carbohydrates for each meal, enter the carbohydrate estimate into the bolus calculator, check and manually enter their BG value into the bolus calculator and administer their meal bolus. For correction boluses, subjects will check and enter their BG value into the bolus calculator and administer their correction bolus. The timing of the bolus delivery will be per each subject's typical dosing routine.
- Consume meals and snacks of their own choosing.
- Subjects may adjust their basal rates or use advanced features such as Temp Basal and Extended Bolus per usual
- Follow their pre-exercise management such as insulin reduction for meal boluses, consumption of snacks, or adjusting their insulin delivery settings
- Treat themselves per their usual routine if they become hypoglycemic or hyperglycemic or have symptoms of either at any time during the study
- Change their CGM per manufacturer's instructions or sooner if necessary
- Change the Pod at least once every 72 hours
- For subjects aged 2-5.9 years of age, parents or trained caregivers will be instructed that they need to be physically present during the decision and delivery of insulin boluses for this age group, as well as be available for glucose monitoring and treatment during the 4-hour post bolus period.

Subjects and caregivers will be reminded to NOT use the system in Automated Mode for the duration of the 14-day study. Any use of automated mode will be considered a protocol deviation.

Subjects not currently enrolled in the Omnipod Horizon™ Pivotal Study (G190270) will be provided, by the site, information regarding treatment of hypoglycemia and hyperglycemia including sick day management and emergency management of severe hypoglycemia and diabetic ketoacidosis. Instructions will be given to subjects on how to contact clinical study staff 24-hours per day to report any study related problems. Subjects will be encouraged to call the clinical study site at any time with any concerns.

8.1.2 Visit 3

Visit 3 will be conducted either over the telephone or in person at the clinical study site on Day 3 ±1d. This visit will include:

- Review of concomitant medications
- Assessment of adverse events
- Assessment of complaints and/or device deficiencies

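### The conditions that waive Visit 2 training, dispensing and safety information contradict each other, and the conflict matters for a 2-5.9-year-old enrolled in the pivotal study but not yet started on it

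*Combined protocol and SAP*

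**What the plan says.** The protocol decides in three ways who receives the Visit 2 steps.

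- **No waiver.** The study schedule overview in the protocol summary says: "Subjects will be trained to use the Manual Mode feature of the system".
- **Enrolment test.** Section 5.2 says: "Subjects not currently enrolled in the Omnipod Horizon™ Pivotal Study (G190270) will train to use the Manual Mode feature of the system". Table 1 footnote f puts the same condition on five rows: glucagon training with hypo/hyperglycemia information, device training, dispensing, removal of the personal pump, and placement of the system. In section 8.1.1 the list of supplies to dispense carries it, and so does the information sentence: "Subjects not currently enrolled in the Omnipod Horizon™ Pivotal Study (G190270) will be provided, by the site, information regarding treatment of hypoglycemia". That sentence goes on to cover hyperglycemia, sick days, and emergency management of severe hypoglycemia and DKA. Table 1 footnote h uses the enrolment test to decide whether Visits 1 and 2 must be in person.
- **Actual-status test.** The Visit 2 bullets in section 8.1.1 look at what has happened. For safety training: "Training on Glucagon administration and information on treatment of hypo/hyperglycemia (if training was not previously performed while participating in the Omnipod Horizon™ Pivotal Study (G190270". For the system: "Omnipod Horizon™ System device training conducted by trained clinical site staff (if training was not previously performed while participating in the Omnipod Horizon™ Pivotal Study". For supply: "Dispense Omnipod Horizon™ System, including CGM (if System was not previously dispensed while participating in the Omnipod Horizon™ Pivotal Study (G190270". Meter quality control depends on prior dispensing. Pump removal and Pod placement depend on whether the system is already in use in Manual Mode, and sensor placement on whether the study CGM is already worn.

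On the youngest cohort, section 7 says: "Subjects aged 2-5.9 may be recruited from the pivotal study but must complete or withdraw from this study before commencement of the Standard Therapy phase". Table 1 footnote g and the note to the screening assessments in section 7.1 describe these children as planning to take part in the pivotal study.

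**The concern.** Enrolment in another study is a stand-in for having been trained and equipped, and it is only as good as the link between the two. Subjects aged 6-70 come from a paused pivotal study that they will resume, so the link is reasonable. Subjects aged 2-5.9 take part here before the first pivotal phase that the protocol names for them, so enrolment there does not show that a caregiver has been trained, supplied or informed.

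The stake is safety instruction in the cohort where the protocol requires a caregiver to be physically present for every bolus decision and delivery. A site working from Table 1, where visit procedures are looked up, could in good faith treat an untrained caregiver as exempt. A site working from the Visit 2 bullets would not.

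**Working it through.** No figure in the plan bears on this, so the check is to apply each rule to each kind of subject.

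| Subject | Summary | Section 5.2, footnote f, supply list, information sentence | Visit 2 bullets in 8.1.1 |
|---|---|---|---|
| (a) Aged 2-5.9, not yet enrolled in the pivotal study | Training required | Steps required | Steps required |
| (b) Aged 2-5.9, enrolled in the pivotal study, not yet trained or supplied there | Training required | Steps waived | Steps required |
| (c) Enrolled, trained and supplied in the pivotal study | Training required | Steps waived | Training and dispensing waived |

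**Case (a).** Both tests require every step. There is no gap.

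**Case (c).** The two tests agree on training and dispensing; only the summary differs, by omitting the exception. Pump removal and placement agree only if the subject is already using the system in Manual Mode. Most of the 6-70 cohorts should fall here, assuming they were trained and supplied before the pause. The documents do not state this for each subject.

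**Case (b).** The conflict is direct. The bullet condition, "if training was not previously performed while participating in the Omnipod Horizon™ Pivotal Study (G190270", is met, so training is due; under footnote f and section 5.2 it is not.

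**What the bullets leave open in case (b).** Even if a site follows the bullets, some items in section 8.1.1 rest on the enrolment test alone:

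- Sick-day management and emergency management of DKA are named only in the information sentence. The bullet names glucagon and treatment of hypo/hyperglycemia.
- Test strips and lancets are named only in the supply list, although Phase 1 calls for a meter value with each meal or correction bolus.
- Under footnote h, Visits 1 and 2 could be by telephone for a child in case (b).

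**Can case (b) occur?** Sections 5.2 and 7 allow recruitment from the pivotal study, which suggests that it can. Footnote g and the section 7.1 note speak of children who plan to join, which suggests case (a). No passage says whether a child recruited from the pivotal study but not started on it counts as currently enrolled.

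**Size.** The cohort is 5 of 30 evaluable subjects (5/30 = 16.7%). The number in case (b) lies between 0 and 5 of these. Up to 42 may be enrolled in all, and that total is not split by age.

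**The case against.** The strongest reply is that the protocol, read as a whole, protects the untrained caregiver. Section 8.1.1 is the operative visit text, and its bullets require safety training, system training and dispensing unless these were already done. Footnote g separates children who plan to participate from subjects already enrolled, so most preschoolers may simply be in case (a). A literal waiver of dispensing and placement would also leave an unsupplied child with nothing to start Phase 1 on, and section 8.2.3 assumes that these children hold devices at the end. Inclusion criterion 5 requires the investigator's confidence that the family can operate the devices, and Visit 3 includes a data review.

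Much of this stands, and it rules out several stronger readings that a reader might reach:

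- **That a preschool child can start with none of these steps required.** Not supported. In case (a) every step applies, and in case (b) the bullets still require training and dispensing.
- **That most of the preschool cohort is affected**, because section 12.7 expects most subjects to be in both studies. Not supported. The 25 subjects aged 6-70 could satisfy that alone (25/30 = 83%), and taking part in both studies is not the same as being enrolled and untrained at Visit 2.
- **That the 24-hour contact instruction is also waived.** It is not. It is a separate sentence with no condition, as is the caregiver-presence instruction.
- **That the waiver wording biases the Phase 1 comparison.** Not shown. Phase 1 comes first for everyone whatever the waiver says, and the documents give nothing from which to attribute an effect to it.

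The reply does not remove the contradiction. Nothing ranks the section 8.1.1 bullets above Table 1 or section 5.2, section 8.1.1 uses both tests itself, and the safeguards named do not replace training or written safety information.

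**Conclusion.** The point holds as an internal inconsistency with a safety bearing, limited to one kind of subject: a 2-5.9-year-old formally enrolled in the pivotal study who has not been trained or supplied there. The conclusion assumes that such a child can exist under the recruitment wording, which the documents allow but do not settle, and that a site might follow Table 1 or section 5.2 rather than the Visit 2 bullets. The extent is 0 to 5 of the 30 planned evaluable subjects and cannot be narrowed from the documents. Sample size and the planned analyses are unaffected. It should be corrected because the exposed items are safety training and information and the correction is almost free.

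**What to change.** Reconcile the summary statement, the section 5.2 sentence, Table 1 footnotes f and h, and the section 8.1.1 supply list and information sentence with the Visit 2 bullets, so that one condition governs all of these steps. Word it in terms of what is documented as completed or supplied for that subject or caregiver, not enrolment status alone, and have the site check and record it at Visit 2. State how a 2-5.9-year-old enrolled in but not started on the pivotal study is classified, and use that term consistently in footnote g and section 7.1. The content of training and all clinical rules remain with the sponsor.

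The cost is wording changes to the summary, one sentence in section 5.2, two table footnotes and two places in section 8.1.1, a definition for the youngest cohort, and a source check at Visit 2. For any caregiver not yet trained, it means a training session that the Visit 2 bullets already call for.
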